8.6 Criteria for Discontinuing Protocol Treatment

Protocol treatment will be continued until any of the criteria for discontinuing protocol treatment is met, and the study will be completed when it is decided to discontinue treatment.

1. Any of the criteria for discontinuing initial treatment (regorafenib for patients in Arm A and anti-EGFR±irinotecan for patients in Arm B) is met, and sequential treatment cannot be resumed within 28 days
2. Any of the criteria for discontinuing sequential treatment (anti-EGFR±irinotecan for patients in Arm A and regorafenib for patients in Arm B) is met.
3. Patient's request for discontinuation of protocol treatment.
4. Treating physician's decision

9.0 Ancillary Treatment/Supportive Care

- 9.1 Antiemetic's may be used at the discretion of the attending physician.
- 9.2 Blood products and growth factors should be utilized as clinically warranted and following institutional policies and recommendations. The use of growth factors should follow published guidelines of the American Society of Clinical Oncology (ASCO) Recommendations for the Use of WBC Growth Factors: American Society of Clinical Oncology Clinical Practice Guideline Update. *J Clin Oncol* 2015;33:3199-3212.
- 9.3 Patients should receive full supportive care while on this study. This includes blood product support, antibiotic treatment, and treatment of other newly diagnosed or concurrent medical conditions. All blood products and concomitant medications such as antidiarrheals, analgesics, and/or antiemetics received from the first day of study treatment administration until 30 days after the final dose will be recorded in the medical records.
- 9.4 Diarrhea: This could be managed conservatively with loperamide. The recommended dose of loperamide is 4 mg at first onset, followed by 2 mg every 2-4

hours until diarrhea free (maximum 16 mg/day).

In the event of grade 3 or 4 diarrhea, the following supportive measures are allowed: hydration, octreotide, and antidiarrheals.

If diarrhea is severe (requiring intravenous rehydration) and/or associated with fever or severe neutropenia (grade 3 or 4), broad-spectrum antibiotics must be prescribed. Patients with severe diarrhea or any diarrhea associated with severe nausea or vomiting **should be hospitalized** for intravenous hydration and correction of electrolyte imbalances.

- 9.5 Prevention and treatment of hand-foot skin reaction
- Use of creams (urea-based or non-ureabased), avoid pressure points, use insole cushions, steroid cream, analgesics, keep rest, etc
 - Symptomatic treatment, including drugs for complications (e.g., ointment and Minomycin for skin symptoms), bisphosphonates, and morphine, can be given simultaneously if there are no interactions with anticancer drugs used.
- 9.6 Unacceptable concomitant therapies/supportive therapies
During the treatment period, chemotherapy other than protocol treatment, radiation therapy, immunotherapy, or surgical therapy should not be given, because protocol treatment may be affected. In addition, no investigational product that may affect protocol treatment is allowed. Avoid to use of strong inhibitors and inducers of CYP3A4. For any other medications that must be carefully administered in combination with protocol treatment, see the package insert.

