ALT increased, amylase increased, anaphylactic like reaction, anaphylaxis, angina, arterial thrombosis, bleeding, bradycardia, cardiac arrest, cerebral infarct, cerebrovascular accident, circulatory failure, colitis, dysrhythmia, embolus, gastrointestinal bleeding, gastrointestinal obstruction, hepatomegaly, hyperglycemia, hypersensitivity, hyponatremia, ileus, interstitial pulmonary disease (IPD), intestinal perforation, ischemic colitis, lipase increased, lymphocytopenia, megacolon, MI, myocardial ischemia, neutropenic typhlitis, pancreatitis, paresthesia, peripheral vascular disorder, pulmonary embolus, pulmonary toxicity (dyspnea, fever, reticulonodular infiltrates on chest x-ray), renal failure (acute), renal impairment, syncope, thrombophlebitis, thrombosis, typhlitis, ulceration, ulcerative colitis

- 15.48 **Drug procurement:** Commercial supplies. Pharmacies or clinics shall obtain supplies from normal commercial supply chain or wholesaler.

15.19 **Nursing Guidelines:**

15.191 Early diarrhea (occurring during or shortly after infusion of CAMPTOSAR) is usually transient and infrequently severe. It may be accompanied by cholinergic symptoms of rhinitis, increased salivation, miosis, lacrimation, diaphoresis, flushing, and intestinal hyperperistalsis that can cause abdominal cramping. Bradycardia may also occur. Early diarrhea and other cholinergic symptoms may be prevented or treated. Consider prophylactic or therapeutic administration of 0.25 mg to 1 mg of intravenous or subcutaneous atropine (unless clinically contraindicated). These symptoms are expected to occur more frequently with higher irinotecan doses. Begin loperamide at the first episode of poorly formed or loose stools or the earliest onset of bowel movements more frequent than normal. One dosage regimen for loperamide is 4 mg at the first onset of late diarrhea and then 2 mg every 2 hours until the patient is diarrhea-free for at least 12 hours. Loperamide is not recommended to be used for more than 48 consecutive hours at these doses, because of the risk of paralytic ileus. During the night, the patient may take 4 mg of loperamide every 4 hours. Patients should contact their physician if any of the following occur: diarrhea for the first time during treatment; black or bloody stools; symptoms of dehydration such as lightheadedness, dizziness, or faintness; inability to take fluids by mouth due to nausea or vomiting; or inability to get diarrhea under control within 24 hours.

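### Section 9.4 caps loperamide at 16 mg/day, while the irinotecan nursing guideline in Section 15.4 gives a schedule with no daily cap that passes 16 mg once dosing runs beyond 12 hours

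*Combined protocol and SAP*

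**What the plan says.** Section 9.4 (Ancillary Treatment/Supportive Care) covers diarrhea without tying it to one study drug. Its first dose and interval, the latter in hours, are stated as follows: "The recommended dose of loperamide is 4 mg at first onset, followed by 2 mg every 2-4". The end point and the daily ceiling come next in that sentence: "hours until diarrhea free (maximum 16 mg/day"). It gives no limit on the number of days and makes no exception for irinotecan.

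The irinotecan drug information in Section 15.4 has its own nursing guideline. It is printed as item 15.191, a number that the regorafenib section also uses. On dose and interval it reads: "One dosage regimen for loperamide is 4 mg at the first onset of late diarrhea and then 2 mg every 2 hours". The stopping point that it names is worded differently from the one in Section 9.4: "until the patient is diarrhea-free for at least 12 hours". For the night it adds: "During the night, the patient may take 4 mg of loperamide every 4 hours". On duration it says: "Loperamide is not recommended to be used for more than 48 consecutive hours at these doses". It states no maximum per day.

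Neither text refers to the other. Under Section 7.0 irinotecan may accompany the anti-EGFR antibody at the treating physician's discretion, so any patient who receives it falls under both texts.

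**The concern.** The starting dose is the same in both places, and the 2-hour interval in Section 15.4 lies within the 2-4 hour range of Section 9.4. The difference is the ceiling: one text sets a daily maximum, and the other describes a schedule that, if continued, goes past it. A site preparing a take-home instruction for a patient on irinotecan finds two sources and nothing that says which governs.

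This matters because Section 15.4 lists late-onset diarrhea among the common irinotecan toxicities (above 10%) and says that it can be life threatening. Diarrhea is also graded at each evaluation (Section 10.52), and grade 3 diarrhea is one of the events that lowers the irinotecan dose (Section 8.432). A clear supportive-care instruction therefore has some bearing on how uniformly this toxicity is handled across sites. The documents do not show what instruction sites actually hand out, so different practice is a possibility and not an established fact.

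**Working it through.** The 16 mg/day in Section 9.4 is a set limit, not a derived figure, so there is nothing to reproduce. The check is to add up the doses under each schedule and compare the totals with that limit.

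**Inputs**
- Section 9.4: 4 mg first, then 2 mg every 2-4 hours; maximum 16 mg/day.
- Section 15.4, irinotecan item 15.191: 4 mg first, then 2 mg every 2 hours; at night 4 mg every 4 hours; until 12 hours free of diarrhea; no more than 48 consecutive hours.

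**Formulas**
- First 24 hours = first dose + repeat dose x number of repeat times before hour 24.
- Later full day = repeat dose x 24 / interval.

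**Totals if dosing continues throughout**

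| Schedule | First 24 h | Later full day |
|---|---|---|
| 9.4, every 4 h | 4 + 5 x 2 = 14 mg | 6 x 2 = 12 mg |
| 9.4, every 3 h, before applying the cap | 4 + 7 x 2 = 18 mg | 8 x 2 = 16 mg |
| 9.4, every 2 h, before applying the cap | 4 + 11 x 2 = 26 mg | 12 x 2 = 24 mg |
| 15.4, every 2 h, no cap stated | 4 + 11 x 2 = 26 mg | 12 x 2 = 24 mg |

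The night option is 4 mg / 4 h = 1 mg/h, the same rate as 2 mg / 2 h. A later full day therefore stays at 24 mg. Depending on where the night falls, the first 24 hours come to 26-28 mg; the upper value arises when the first 4 mg night dose is taken two hours after the last daytime dose.

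**Size against the cap.** 26 / 16 = 1.625, about 63% above. 24 / 16 = 1.5, or 50% above. The excess is 10 mg and 8 mg.

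**When the cap is passed.** With 2-hourly dosing the running total at hour 12 is 4 + 6 x 2 = 16 mg. The next dose, at hour 14, makes 18 mg. At hour 12 the Section 9.4 cap stops dosing for that day; the Section 15.4 schedule has no such stop.

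**How long an episode must last.** The requirement of 12 diarrhea-free hours extends dosing beyond the last loose stool.
- Last loose stool at the first dose: dosing runs to hour 12. Total 4 + 5 x 2 = 14 mg, or 16 mg if the hour-12 dose is taken. The cap is not exceeded.
- Last loose stool at hour 4: dosing runs to hour 16. Total 4 + 7 x 2 = 18 mg before that hour. The cap is exceeded.

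An episode still active about four hours after the first dose is enough; a full day of diarrhea is not needed.

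**Effect of the 48-hour limit.** It bounds the duration but not the daily total. Over 48 hours the 2-hourly schedule gives 4 + 23 x 2 = 50 mg, against 2 x 16 = 32 mg under the cap.

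**The case against.** The best answer is that these are not two rival orders. Section 9.4 says only that diarrhea could be handled this way and calls its dose recommended. Section 15.4 presents its schedule as one possible regimen, says what the patient may take at night, and sits under a heading that sends the reader to the package insert. The general section covers any study drug; the nursing item concerns late diarrhea from an optional drug. The 24-26 mg totals are printed nowhere: they follow only if dosing continues all day. There are also safeguards. Patients are told to contact their physician at the first diarrhea, or if it is not controlled within 24 hours, and Section 9.4 calls for hospitalization when diarrhea is severe.

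Much of this stands, and it rules out two stronger readings. A reader might infer that following either text means departing from the other. The documents do not support that: a patient kept within the Section 9.4 maximum breaches nothing in Section 15.4, which only offers an option. A reader might also infer that the stopping points and durations contradict each other. They do not: 12 diarrhea-free hours can be read as spelling out what being free of diarrhea means, and silence in Section 9.4 on duration does not conflict with a 48-hour limit elsewhere.

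What the objection does not remove is the ceiling. A stated maximum is the firmest term in Section 9.4, irinotecan is not exempted from it, and the other text describes dosing that can go beyond it. Advisory wording and the safeguards soften the consequence without telling a site which total applies.

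**Conclusion.** The inconsistency is real, limited and one-way. Following the irinotecan nursing guideline beyond hour 12 takes the patient past the Section 9.4 maximum, by 10 mg in the first 24 hours and 8 mg in a later full day if dosing is uninterrupted. This rests on three assumptions: the daily maximum is counted over 24 hours from the first dose; doses are taken at the stated intervals without a break; and Section 9.4 applies to irinotecan-related diarrhea, since nothing in it says otherwise.

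Severity is moderate. It is a question of consistency between two guidance texts on a safety matter, not a calculation error. It should not be read as a flaw in the trial's design: study-drug dosing, eligibility, randomization, endpoints, sample size, alpha, power and the stopping rule are unaffected. Nothing here says which loperamide figures are right.

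**What to change.** Reconcile Section 9.4 with the irinotecan nursing guideline in Section 15.4. Keep a single loperamide instruction and have the other section refer to it. The instruction should make clear whether a daily maximum applies to patients on irinotecan. The stopping point and the limit on duration, now given in full only in Section 15.4, should be aligned at the same time. The clinical team decides which figures stand. Because item number 15.191 appears under both regorafenib and irinotecan, the cross-reference should name the drug, or the irinotecan items should be renumbered.

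The cost is one wording change in the protocol and a matching change to any site or patient instruction. No analysis or design element has to be revisited.

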10.0 Adverse Event (AE) Reporting and Monitoring

Definitions

Adverse Event

Any untoward medical occurrence associated with the use of a drug in humans, whether or not considered drug related.

Suspected Adverse Reaction

Any adverse event for which there is a reasonable possibility that the drug caused the adverse event.

Expedited Reporting

Events reported to sponsor within 24 hours, 5 days or 10 days of study team becoming aware of the event.

Routine Reporting

Events reported to sponsor via case report forms

Events of Interest

Events that would not typically be considered to meet the criteria for expedited reporting, but that for a specific protocol are being reported via expedited means in order to facilitate the review of safety data (may be requested by the FDA or the sponsor).

10.1 Adverse Event Characteristics

CTCAE term (AE description) and grade: The descriptions and grading scales found in the revised NCI Common Terminology Criteria for Adverse Events (CTCAE) version 5.0 will be utilized for AE reporting. All appropriate treatment areas should have access to a copy of the CTCAE version 5.0. A copy of the CTCAE version 5.0 can be downloaded from the CTEP web site:

[REDACTED]

- a. Adverse event monitoring and reporting is a routine part of every clinical trial.
- b. Identify the grade and severity of the event using the CTCAE version 5.0
- c. Determine whether the event is expected or unexpected (see Section 10.2).
- d. Determine if the adverse event is related to the study intervention (agent, treatment or procedure) (see Section 10.3).
- e. Determine whether the event must be reported as an expedited report. If yes, determine the timeframe/mechanism (see Section 10.4).
- f. Determine if other reporting is required (see Section 10.5).
- g. Note: All AEs reported via expedited mechanisms must also be reported via the routine data reporting mechanisms defined by the protocol (see Sections 10.53 and 18.0).

Each CTCAE term in the current version is a unique representation of a specific event used for medical documentation and scientific analysis and is a single MedDRA Lowest Level Term (LLT).

NOTE: A severe AE, as defined by the above grading scale, is NOT the same as serious AE which is defined in the table in Section 10.4.

10.2 Expected vs. Unexpected Events

Expected events - are those described within the Section 15.0 of the protocol, the study specific consent form, package insert (if applicable), and/or the investigator brochure, (if an investigator brochure is not required, otherwise described in the general investigational plan).

Unexpected adverse events or suspected adverse reactions are those not listed in Section 15.0 of the protocol, the study specific consent form, package insert (if applicable), or in the investigator brochure (or are not listed at the specificity or severity that has been observed); if an investigator brochure is not required or available, is not consistent with the risk information described in the general investigational plan.

Unexpected also refers to adverse events or suspected adverse reactions that are mentioned in the investigator brochure as occurring with a class of drugs but have not been observed with the drug under investigation.

10.3 Assessment of Attribution

When assessing whether an adverse event is related to a medical treatment or procedure, the following attribution categories are utilized:

Definite - The adverse event is *clearly related* to the agent(s)/treatment.

Probable - The adverse event is *likely related* to the agent(s)/treatment.

Possible - The adverse event *may be related* to the agent(s)/treatment.

Unlikely - The adverse event is *doubtfully related* to the agent(s)/treatment.

Unrelated - The adverse event is *clearly NOT related* to the agent(s) treatment.

Events determined to be possibly, probably or definitely attributed to a medical treatment suggest there is evidence to indicate a causal relationship between the drug/device and the adverse event.

10.31 EXPECTED Serious Adverse Events: Protocol Specific Exceptions to Expedited Reporting

For this protocol only, the following Adverse Events/Grades are expected to occur within this population and do not require Expedited Reporting. These events must still be reported via Routine Reporting (see Section 10.53). *

Note: These exceptions only apply if the adverse event does not result in hospitalization.

If the adverse event results in hospitalization, then the standard expedited adverse events reporting requirements must be followed.

System Organ Class (SOC)	Adverse event/ Symptoms	CTCAE Grade at which the event will not be expeditedly reported.
Gastrointestinal Disorders	Diarrhea Dyspepsia Nausea Vomiting Colitis Pancreatitis	Any Grade
General disorders and administrations site conditions	Anorexia General disorders and administrations site conditions- Other (Asthenia) Dehydration Fatigue Malaise Weight loss	Grades 1-3
Hepatobiliary disorders	Cholecystitis	Any Grade
Infections and infestations	Lung Infection Sinusitis Skin infection Urinary tract infection	Grades 1-3
Investigations	Alkaline phosphatase increased Alanine aminotransferase increased Aspartate aminotransferase increased Lymphocyte count decreased	Any Grade

Metabolism and nutrition disorders	Hyperkalemia	Any Grade
	Hypocalcemia	
	Hypomagnesemia	
	Hyponatremia	
Musculoskeletal and connective tissue disorders	Arthralgia	Any Grade
	Back pain	
	Musculoskeletal and connective tissue disorder – Other (muscle spasms)	
Skin and subcutaneous tissue disorders	Alopecia	Any Grade
	Rash acneiform	
	Rash maculo-papular	
	Palmar-plantar erythrodysesthesia syndrome	

*Report any clinically important increase in the **rate** of a serious suspected adverse reaction (at your study) site over that which is listed in the protocol or investigator brochure as an expedited event.

*Report an expected event that is greater in severity or specificity than expected as an expedited event

*An investigational agent/intervention might exacerbate the expected AEs associated with a commercial agent. Therefore, if an expected AE (for the commercial agent) occurs with a higher degree of severity or specificity, expedited reporting is required.

A list of known/expected AEs is reported in the investigator brochure, package insert or the literature, including AEs resulting from a drug overdose.

10.312 Death

- Any death occurring within 30 days of the last dose, regardless of attribution to an agent/intervention under an IND/IDE requires expedited reporting within 24-hours.
- Any death occurring greater than 30 days with an attribution of possible, probable, or definite to an agent/intervention under an IND/IDE requires expedited reporting within 24-hours.
- **Reportable categories of Death**
 - Death attributable to a CTCAE term.
 - Death Neonatal: A disorder characterized by cessation of life during the first 28 days of life.
 - Death NOS: A cessation of life that cannot be attributed to a CTCAE term associated with Grade 5.
 - Sudden death NOS: A sudden (defined as instant or within one hour of the onset of symptoms) or an unobserved cessation of life that cannot be attributed to a CTCAE term associated with Grade 5.
 - Death due to progressive disease should be reported as Grade 5 “Disease Progression” under the (SOC) General Disorders and Administration Site Conditions. Evidence that the death was a manifestation of underlying disease (e.g., radiological changes suggesting tumor growth or progression: clinical deterioration associated with a disease process) should be submitted.

10.313 Secondary Malignancy

- A **secondary malignancy** is a cancer caused by treatment for a previous malignancy (e.g., treatment with investigational agent/intervention, radiation or chemotherapy). A secondary malignancy is not considered a metastasis of the initial neoplasm.
- All secondary malignancies that occur following treatment with an agent under an IND/IDE to be reported. Three options are available to describe the event:
 - Leukemia secondary to oncology chemotherapy (e.g., Acute Myelocytic Leukemia [AML])
 - Myelodysplastic syndrome (MDS)
 - Treatment-related secondary malignancy
- Any malignancy possibly related to cancer treatment (including AML/MDS) should also be reported via the routine reporting mechanisms outlined in each protocol.

10.314 Second Malignancy

- A second malignancy is one unrelated to the treatment of a prior malignancy (and is NOT a metastasis from the initial malignancy). Second malignancies require ONLY routine reporting.

10.315 Pregnancy

Prior to obtaining private information about a pregnant woman and her infant, the investigator must obtain consent from the pregnant woman and the newborn infant's parent or legal guardian before any data collection can occur. A consent form will need to be submitted to the IRB for these subjects if a pregnancy occurs. If informed consent is not obtained, no information may be collected.

In cases of fetal death, miscarriage or abortion the mother is the patient. In cases where the child/fetus experiences a serious adverse event other than fetal death, the child/fetus is the patient.

NOTE: When submitting ACCRU Adverse Event Report reports for “Pregnancy”, “Pregnancy loss”, or “Neonatal loss”, the potential risk of exposure of the fetus to the investigational agent(s) or chemotherapy agent(s) should be documented in the “Description of Event” section. Include any available medical documentation. The funding sponsor will be notified by ACCRU within 24 hours of notification.

10.4 Expedited Reporting Requirements for Studies using Commercial Agent(s) ONLY:

Expedited Reporting Requirements for Adverse Events that Occur in a Non-IND/IDE trial within 30 Days of the Last Administration of a Commercial Agent^{1,2}**FDA REPORTING REQUIREMENTS FOR SERIOUS ADVERSE EVENTS (21 CFR Part 312)**

NOTE: Investigators **MUST** immediately report to the sponsor **ANY** Serious Adverse Events, whether or not they are considered related to the investigational agent(s)/intervention (21 CFR 312.64)

An adverse event is considered serious if it results in **ANY** of the following outcomes:

- 1) Death
- 2) A life-threatening adverse event
- 3) An adverse event that results in inpatient hospitalization or prolongation of existing hospitalization for \geq 24 hours
- 4) A persistent or significant incapacity or substantial disruption of the ability to conduct normal life functions
- 5) A congenital anomaly/birth defect.
- 6) Important Medical Events (IME) that may not result in death, be life threatening, or require hospitalization may be considered serious when, based upon medical judgment, they may jeopardize the patient or subject and may require medical or surgical intervention to prevent one of the outcomes listed in this definition. (FDA, 21 CFR 312.32; ICH E2A and ICH E6).

ALL SERIOUS adverse events that meet the above criteria **MUST** be immediately reported to the sponsor within the timeframes detailed in the table below.

Hospitalization	Grade 1 Timeframes	Grade 2 Timeframes	Grade 3 Timeframes	Grade 4 & 5 Timeframes
Resulting in Hospitalization \geq 24 hrs		7 Calendar Days		24-Hour 3 Calendar Days
Not resulting in Hospitalization \geq 24 hrs	Not required		7 Calendar Days	

Expedited AE reporting timelines are defined as:

- “24-Hour; 3 Calendar Days” - The AE must initially be reported via MedWatch within 24 hours of learning of the AE, followed by a complete expedited report within 3 calendar days of the initial 24-hour report.
- “7 Calendar Days” - A complete expedited report on the AE must be submitted within 7 calendar days of learning of the AE.

¹Serious adverse events that occur more than 30 days after the last administration of investigational agent/intervention and have an attribution of possible, probable, or definite require reporting as follows:

Expedited 24-hour notification followed by complete report within 3 calendar days for:

- All Grade 4, and Grade 5 AEs

Expedited 7 calendar day reports for:

- Grade 2 adverse events resulting in hospitalization or prolongation of hospitalization
- Grade 3 adverse events

² For studies using PET or SPECT IND agents, the AE reporting period is limited to 10 radioactive half-lives, rounded UP to the nearest whole day, after the agent/intervention was last administered. Footnote “1” above applies after this reporting period.

Effective Date: May 5, 2011

Additional Instructions:

1. An increased incidence of an expected adverse event (AE) is based on the patients treated for this study at their site. A list of known/expected AE's are reported in the package insert or the literature, including AE's resulting from a drug overdose.
2. Follow site-specific reporting guidelines.
3. All SAEs occurring after start of administration of regorafenib, regardless of their causal relationship to the study drug shall immediately, within 24 hours at the latest, be reported. Submit a complete FDA 3500A MedWatch form and all deidentified supporting documents to Bayer by fax: [REDACTED]

[REDACTED] The FDA 3500A MedWatch form can be found at [REDACTED]

[REDACTED] or on the ACCRU web site along with the MedWatch Fax Cover Sheet (found on the ACCRU website).

Also submit the MedWatch form 3500A to the ACCRU SAE Coordinator by email at [REDACTED]

3. The ACCRU IND Coordinator will assist the sponsor-investigator in notifying the FDA if required.

